12.5 Analysis of secondary endpoints

12.5.1 Efficacy endpoint(s)

Secondary efficacy endpoints include:

- 1. Composite of BPAR, graft loss, death
- 2. Composite of BPAR, graft loss, death, lost to follow-up

- 3. Treated BPAR (tBPAR)
- 4. Acute rejection (AR)
- 5. Treated AR
- 6. Antibody-mediated rejection (AMR)
- 7. Steroid resistant, steroid treated, and antibody treated AR
- 8. Steroid resistant, steroid treated, and antibody treated BPAR
- 9. Graft loss
- 10. Death
- 11. Graft loss and death

Simple event rates (proportions of events) will be presented. In addition, the event rates will be estimated with Kaplan-Meier estimates. Greenwood's formula will be used to estimate the variance and to derive 2-sided 95% Z-test based confidence intervals for the difference between a CFZ533 and control arm.

The confidence interval will be constructed as:

$$(r_{T_i} - r_C) \pm Z_{\alpha/2} * SE_{d_i}$$

where

 r_{T_i} = Kaplan-Meier estimate of the failure rate for CFZ533 arm up to 12 months, i = 1, 2,

 r_c = Kaplan-Meier estimate of the failure rate for the control arm up to 12 months,

$$SE_{d_i} = \sqrt{SE_{T_i}^2 + SE_C^2}, i = 1, 2,$$

 SE_{T_i} = Estimated standard error for CFZ533 arm based on Greenwood's formula, i = 1, 2,

 SE_c = Estimated standard error for the control arm based on Greenwood's formula, and $\alpha = 0.05$.

12.5.2 Safety endpoints

12.5.2.1 Renal function

The key secondary objective is to evaluate renal function (eGFR) at Month 12. GFR will be estimated using the MDRD formula described in Section 16.4.

Central laboratory serum creatinine values will be used for all renal function data analysis. If the central lab value is missing, then the local creatinine value will be used, if available.

The estimand is:

- 1. population: Full analysis set (FAS)
- 2. endpoint: change from randomization in eGFR at 12 months post-transplant
- 3. **intercurrent events**: regardless of missing assessments, discontinuation of study treatment, graft loss, or loss-to-follow-up

4. **summary measure**: the difference in mean eGFR on CFZ533 at 12 months post-transplant as compared to control

The mean change for each arm will be obtained through covariate-adjusted treatment effects using MMRM. The model will contain treatment arm, visit, treatment arm*visit, and randomization GFR with unstructured covariance matrix. The estimand will be evaluated in the FAS population by comparing the difference in mean change between each CFZ533 arm and control.

Renal function at Month 24 measured by eGFR will also be evaluated following the same analyses strategy.

Hypothesis testing

The objective is to demonstrate that either CFZ533 treatment arm is superior to the control arm with respect to mean change in eGFR at 12 months post-transplant.

The null hypothesis: the mean change from randomization in eGFR for a CFZ533 treatment arm is not superior to that in the control arm.

The alternative hypothesis: the mean change from randomization in eGFR for a CFZ533 treatment arm is superior to that in the control arm.

The null hypothesis will be tested at a significance level of 10% against a one-sided alternative hypothesis, and the test statistic will be the estimated difference in Month 12 least squares means from the mixed effects model to allow for adjustment for correlations between time points within participants.

Handling of missing values/censoring/discontinuations

The primary analysis is based on the FAS, i.e., all observations whether on- or off-treatment. Since participants continue to be followed after early study drug discontinuation, the number of missing values is expected to be limited.

- 1. For participants with graft loss or death, a value of 0 will be imputed after the time of graft loss.
- 2. Participants who are lost to follow-up with a functioning graft, or have missing assessments will have missing values assessed via MMRM.

Supportive analyses

The analysis of eGFR (MDRD-4) will be repeated with assessments occurring after discontinuation of study medication counting as missing in the MMRM model (an "on-treatment" analysis).

12.5.2.2 General safety

For all other safety analyses, the safety set will be used. Adverse events (AEs) will be presented and summarized for all treatment-emergent events, with a start date after randomization, whether on- or off-treatment. In addition, a separate summary for death including on treatment and post treatment deaths will be provided. General safety summaries (tables, figures) will

Novartis	Confidential	Page 115 of 136
Amended Clinical Trial Protocol (Version No.	04 clean)	Protocol No. CCFZ533A2202

include only data from the on-treatment period with the exception of baseline data which will also be summarized where appropriate (e.g. change from baseline summaries).

For CFZ533, the on-treatment period lasts from the date of first administration of study treatment to 14 days after the date of the last actual administration. For TAC, it lasts to the day of the last actual administration.

Adverse events

All information obtained on adverse events will be displayed by treatment group.

The number and percentage of participants with treatment emergent adverse events and serious adverse events (events started after the first dose of study medication or events present prior to start of treatment but increased in severity based on preferred term) will be summarized in the following ways:

- by treatment, primary system organ class and preferred term.
- by treatment, primary system organ class, preferred term and maximum severity by treatment, Standardized MedDRA Query (SMQ) and preferred term.

Separate summaries will be provided for study medication related adverse events, death, serious adverse events, other significant adverse events leading to discontinuation and adverse events leading to dose adjustment.

In addition, the proportion of participants with infections will be summarized as follows:

- 1. Infections by type of infection (viral, fungal, bacterial, others) and microorganism of infection
- 2. Serious infections by type of infection (viral, fungal, bacterial, others) and microorganism of infection

The incidence rate of infection by type and micro-organism will be tabulated for each treatment arm. The key safety parameter is serious infections. The number of serious infections will be used to evaluate the stopping rule as outlined in Section 9.1.5.

AEs and infections data will be analyzed as a whole under the heading of AEs for each treatment arm. If a participant has multiple occurrences of an AE, the participant will only be counted once in the corresponding AE category. If participant has multiple AEs within a SOC, the participant will be counted only once for that SOC. If a participant has multiple severity ratings for an AE, the participant will be counted under the maximum rating.

New onset of diabetes mellitus (NODM)

The new onset diabetes mellitus is defined in Section 8.4.4

If any of the criteria for diabetes prior transplantation is unknown (e.g., lab values) and all other criteria are true, the subject will be considered to have no diabetes pre-transplant.

The proportion of participants developing new onset diabetes mellitus after transplantation (NODM) will be summarized by treatment arm. The probabilities of developing NODM will be compared between treatment arms at Month 12 and at Month 24 post-transplantation using logistic regression models with treatment arm and HbA1c levels at randomization as explanatory variables. Death, graft loss, or loss to follow up without NODM before Month 12

(or 24) will not be counted as developing NODM. This analysis will be performed using participants in the FAS population who do not have diabetes mellitus at randomization.

Vital signs

Summary statistics will be provided by treatment and visit/time.

12-lead ECG

All ECG data will be listed by treatment arm, participant and visit/time. Summary statistics will be provided by treatment and visit/time.

Clinical laboratory evaluations

Summary statistics (mean, standard deviation, minimum, median, maximum) of quantitative lab variables, including change from randomization, will be provided by parameter, treatment, and visit.

Renal function will be plotted over time.

12.5.2.3 Other safety evaluations

Immunogenicity

Blood samples for immunogenicity testing will be collected from all CFZ533-treated participants only, at selected time points, as defined in the assessment schedule (Table 8-1, Table 8-2 and Table 8-3). The presence of anti-CFZ533 antibodies will be assessed using screening and confirmatory assays. An integrated PK/PD and immunogenicity approach, focusing on the clinical and functional consequences of ADA will be applied. The consequences of an immune response to CFZ533 may be correlated with a loss of exposure (free CFZ533 measures), a loss of target engagement (sCD40 measures), and/or the appearance of immune related adverse events.

All immunogenicity results will be listed by treatment arm, participant, and visit/time point. No summary statistics will be provided.

12.5.3 Pharmacokinetics

CFZ533 plasma concentration data will be listed by treatment, participant, and visit/sampling time point. Descriptive summary statistics will be provided by treatment and visit/sampling time point, including the frequency (n, %) of concentrations below the LLOQ.

Summary statistics will include mean (arithmetic and geometric), SD, CV (arithmetic and geometric), median, minimum and maximum. Concentrations below LLOQ will be treated as zero in summary statistics. A geometric mean will not be reported if the dataset includes zero values.

Summary statistics and graphical analysis (e.g. Box-plot) will be provided to compare steadystate PK before and after introduction of PFS in the study. If data permit, PK parameters will be calculated as described in Section 8.5.1 and will be listed by treatment and participant. Descriptive summary statistics will include mean (arithmetic and geometric), SD, and CV (arithmetic and geometric), median, minimum and maximum.

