It is associated with end-stage liver disease and portal hypertension. It is expected to resolve with a liver transplantation, but ascites can also be removed by large volume paracentesis or surgical drainage.

Ascites occurs with moderate volume (< 0.25 L/day) in the majority of liver transplant recipients, but a non-negligible proportion of participants (7%) present with a median volume of 1 L/day for a median duration of 77 days post transplantation (Cirera et al, 2000).

Ascites has the potential to affect CFZ533 exposure in particular if ascites are removed after paracentesis or surgery. The drug loss depends on the amount of ascites removed, and on the drug concentration in the ascites.

In the context of this study, drained ascites will be considered relevant when the cumulative volume of ascites or fluid loss through paracentesis/surgical drainage collected from a participant reaches a cumulative volume of 4 L (similar to belatacept liver transplant study; Klintmalm 2014). CFZ533 compensation will be administered as described in Section 6.1.4.

[figure not shown]
Figure 4-2 displays the predicted CFZ533 plasma exposure during 2 weeks post first dose of CFZ533 on Day 8:

[figure not shown]
- in case of no ascites (light gray),
- in case of ascites and no additional/compensating CFZ533 dose (pink),
- in case of ascites with an additional/compensating CFZ533 dose each time the cumulative ascites volume reaches 4 L (blue).

As shown in Figure 4-2 where two scenarios of ascites drainage are presented (0.5 and 4 L/day), the additional/compensating intravenous dose is expected to adjust the participants' exposure adequately during the first days of treatment.

After Day 29, when CFZ533 concentrations are approaching steady state, a compensating dose specific to the treatment arm (10 mg/kg IV and 5 mg/kg IV in Arm 2 and Arm 3, respectively) should bring the concentration in the range of their respective steady state exposure (not shown).

Note: Until Month 24, each time an additional/compensating intravenous CFZ533 dose (10 or 5 mg/kg) will be administered; a pre-dose blood sample will be taken to assess the CFZ533 concentration in plasma.

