6.1.4 Compensation for CFZ533 loss through ascites fluid drainage

At any time during the treatment period, when the **cumulative** ascites fluid drainage volume reaches at least 4 L, and **independently of the planned dosing schedule** (IV or SC; Section 4.3), an **additional** dose of CFZ533 will be administered intravenously to compensate for the amount of CFZ533 removed from the body through drained ascites.

- Arm 2 (600 mg regimen): one (additional) dose of 10 mg/kg IV CFZ533, regardless of the time
- Arm 3 (300 mg regimen)
 - a. Up to Day 29: one (additional) dose of 10 mg/kg IV CFZ533,
 - b. After Day 29: one (additional) dose of 5 mg/kg IV CFZ533.

In an extreme situation (massive ascites; Cirera 2000) where participants are experiencing a loss of fluid of 4 L/day, this should trigger the daily administration of an additional, compensatory CFZ533 dose, as described above.

Any additional IV dose of CFZ533, administered on top of the scheduled CFZ533 doses (IV, SC), to compensate for drug loss through ascites drainage, should be captured in the appropriate CRF.

Each time an additional/compensating intravenous CFZ533 dose (10 or 5 mg/kg IV) will be administered; a pre-dose blood sample will be taken.

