12.4.1 Definition of primary endpoint

The primary efficacy endpoint is occurrence of composite efficacy failure (BPAR, graft loss, or death) at 12 months post-transplantation based on central pathologist evaluation. If the central pathologist's evaluation is not available, the local pathologist's reading will be used. The estimand is:

- 1. Population: full analysis set
- 2. Endpoint: composite efficacy failure at 12 months
- 3. Intercurrent events: regardless of treatment or study discontinuation, loss to follow-up, or ascites-based dosing adjustment
- 4. Summary measure: the difference in the proportion of participants with composite efficacy failure in a CFZ533 arm compared to control

Note that ascites-based dosing adjustment is not considered a rescue medication because the occurrence of ascites is not due to lack of efficacy. Accordingly, administering CFZ533 to compensate for drug loss caused by ascites cannot be considered rescue medication. In addition, this unscheduled administration will not result in exposure higher than that seen in participants with no ascites.

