2.1.2 Analysis sets

The screened set (SCR) consists of all participants who signed the informed consent. The screened set includes only uniquely screened participants, i.e., in the case of re-screened participants, only the chronologically last screened data is counted. Screening phase disposition will be based on the SCR.

The randomized set (RND) consists of all participants who signed the informed consent and were randomized, including misrandomizations.

The full analysis set (FAS) will include all participants who were transplanted and randomized, excluding mis-randomized participants. Mis-randomized participants are defined as cases where IRT contacts were made by the Investigator/qualified site staff either prematurely or inappropriately to confirmation of the participant's final randomization eligibility and treatment was not administered to the participant. Following the intention-to-treat (ITT) principle, participants will be analyzed according to their treatment assignment at randomization. Participant demographics, baseline characteristics, efficacy and renal function measured by GFR will be performed on the FAS.

The safety set (SAF) consists of all participants in FAS who received at least one dose of study drug (i.e., at least one dose of TAC after randomization in the Control arm and at least one dose of CFZ533 in the CFZ533 arms). Participants will be analyzed according to the treatment they actually received. All safety analyses, including renal function parameters other than GFR, will be performed on the SAF using on-treatment (between start and end of treatment defined in Section 2.1.1) data unless otherwise specified.

The PK analysis set (PKS) will include all participants with at least one available valid (i.e., not flagged for exclusion) PK concentration measurement, who received any study drug and with no protocol deviations that impact on PK data, e.g. if a dose was taken more than 7 days after the planned date.

The total screened participants and each analysis population above will be summarized in terms of the frequencies and percentages. Listings of randomized participants and of the participants excluded from analysis sets will be provided.

Rules for exclusion from analysis sets is in Table 5-9.

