2.8 Pharmacokinetic endpoints

CFZ533 plasma concentration data will be listed by treatment, participant, and visit/sampling time point using PKS. Concentrations will be given in mass per volume units. Descriptive summary statistics will be provided by treatment and visit/sampling time point, including the frequency (n, %) of concentrations below the LLOQ.

Summary statistics will include mean (arithmetic and geometric), SD, CV (arithmetic and geometric), median, minimum, maximum, and 25% and 75% percentiles. Concentrations below LLOQ will be treated as zero in summary statistics. A geometric mean will not be reported if the dataset includes zero values. Summary statistics and graphical analysis (e.g., box plot) will

be provided to compare steady-state PK before and after introduction of PFS in the study. PK is considered steady after 10 weeks since PFS introduction.

If data permit, PK parameters will be calculated as described in Section 8.5.2 in Protocol and will be listed by treatment and participant. Descriptive summary statistics will include mean (arithmetic and geometric), SD, CV (arithmetic and geometric), median, minimum, maximum, and 25% and 75% percentiles.

In addition, CFZ533 concentration will be measured in any collected/drained ascites. The detailed methods and analysis will be described in the Bioanalytical Data Report.

In the zz.xpt file in GPSII (merge file), PK concentration (free CFZ533 in plasma) will be expressed in unit 'microgram/mL' (in addition to 'nanogram/mL'), and time will be expressed in unit 'day' (in addition to 'hours').

- a. Two variables for the elapsed time (*e.g.* EACLTM_1 and EACLTM_2) will be provided: elapsed time since first dose: EACLTM_1 is calculated using the Dose Reference ID provided in the Blood Log under Dose Reference ID series #1,
- b. EACLTM_2 is calculated using using the Dose Reference ID provided in the Blood Log under Dose Reference ID series #2; e.g. for Arm 2 (600 mg Q2W regimen) a Dose Reference ID of 17 for pre-dose PK Sample 115 on Day 225 (17ith dose of CFZ533) means that the elapsed time is calculated with reference to timing of 17ith dose of CFZ533 (and is negative).

The zz.xpt file in GPSII will combine PK data (free CFZ533 in plasma) as well as sCD40 data in plasma (PD). Similar to PK output, elapsed time variables (EACLTM_1 and EACLTM_2) will be generated.

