5.1 Analysis visit windows

Analysis visit windows will be used to summarize the data by visit and are defined in terms of weeks. These will be based on the study schedule of evaluation and comprised a set of days "around" the nominal visits. Analysis visit windows are non-overlapping. All together they cover the entire study period. They are aligned to the dosing regimen, which is every 2 weeks, meaning a month is targeted to cover 4 weeks or 28 days.

As participants do not necessarily have their examinations at the exact scheduled time, it might be misleading if all data with the same nominal visit number are lumped together for a by-visit analysis. Thus, all data (including reported unscheduled assessments) are "re-aligned" according to the window schema given below. Note that the visit windows defined in the protocol are used to guide investigators whereas the 're-aligned' analysis visit windows (simply called visit windows in the following) will be used for the analyses.

Re-aligned visit	Visit window	Relative to first treatment date			
	(relative to date of Tx)	Start day of Visit window	Midpoint	End day of visit window	
1	Screening	Day of informed consent		Day of transplant 1	
2	Baseline	Day of Tx		Day of Tx	
3	Randomization	Day of Tx +1		Start of study drug [#] = Day 1	
4	Day 15	2	8	11	
5	Day 22	12	15	18	
6	Day 29	19	22	29	
7	Month 1.5	30	36	43	
8	Month 2	44	50	57	
9	Month 2.5	58	64	71	
10	Month 3	72	78	85	
11	Month 3.5	86	92	99	
12	Month 4	100	106	113	

Table 5-1	Analysis	visit	windows

For business use only

Novartis SAP

Re-aligned visit	Visit window	Relativ	e to first treatme	ent date
	(relative to date of Tx)	Start day of Visit window	Midpoint	End day of visi window
13	Month 4.5	114	120	127
14	Month 5	128	134	141
15	Month 5.5	142	148	155
16	Month 6	156	162	190
17	Month 8	191	218	246
18	Month 10	247	274	302
19	Month 12	303	330	372 (358*)
20	Month 15	373	414	456
21	Month 18	457	498	540
22	Month 21	541	582	624
23	Month 24	625	666	708
24	Month 27	709	750	792
25	Month 30	793	834	876
26	Month 33	877	918	960
27	Month 36	961	1002	1044
28	Month 39	1045	1086	1128
29	Month 42	1129	1170	1212
30	Month 45	1213	1254	1296
31	Month 48	1297	1338	1380
32	Month 51	1381	1422	1464
33	Month 54	1465	1506	1548
34	Month 57	1549	1590	1632
35	Month 60	1633	1674	1716
36	Month 63	1717	1758	1800
37	Month 66	1801	1842	1884
38	Month 69	1885	1926	1968
39	Month 72	1969	2010	End of study

Day 1 = randomization day if a participant was randomized but did not receive study drug.

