* For all Month 12 analyses, the end of visit window of Month 12 visit is Day 358, instead of Day 372.

Under this window schema, multiple records of a participant are re-aligned into the same visit as follows:

- For post-randomization continuous values (except for CFZ533, TAC, and MMF trough level measurements and liver tests), for a given participant, if multiple numeric measurements for a given variable are reported in the same visit window (e.g., Month 6), then the measurement closest to the target visit day will be taken; if tie, take the earlier measurement. For screening visit, the target day is day of transplant – 1; for baseline, day of transplant; for randomization, start of study drug (Day 1); for other visits, the midpoint of the visit window.
- For trough levels, the last value observed within a visit window is taken.

- For liver tests (bilirubin, SGOT, SGPT, GGT, and alkaline phosphatase), the following algorithm is applied:
 - a. If an acute rejection occurs within a visit window with multiple liver tests reported, the time of the event is the date rejection first suspected, and the liver test to be summarized are the closest to that event (if tie, take the earlier one)
 - b. If no rejection occurs, the assessment closest to the target day is taken.
- For categorical values, the worst value of all records observed in the visit window is used.

For parameters which are not collected at every scheduled visit

, visit windows defined in Table 5-1 will be combined using the following rules for an applicable visit post randomization: "lower limit" of the combined window= "upper limit of prior applicable visit" + 1, "upper limit" of the combined window = "target day of current visit" + integer part of [("target day of next applicable visit" – "target day of current visit")/2]. For example, if a parameter is measured only at Randomization, Day 29 (Month 1), Month 3, Month 6, and Month 12, the combined Day 29 (Month 1) visit window will be from Day 2 to Day 50 (= Day 22 + interger part of [(78 - 22)/2]), Month 3 will extend from Day 51 to Day 120 (= Day 78 + interger part of [(162 - 78)/2]), etc.. If more than one assessment falls into the combined window, the rules defined above handling multiple records are applied.

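### SAP 5.1's last-value rule lets off-schedule samples drawn before compensatory CFZ533 doses replace scheduled troughs in the by-visit PK summaries

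*Protocol*

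**What the plan says.** **The extra sample.** Under Protocol 4.3 and 6.1.4, an additional IV dose of CFZ533 is given in either CFZ533 arm each time cumulative drained ascites reaches at least 4 L, independently of the dosing schedule. "Each time an additional/compensating intravenous CFZ533 dose (10 or 5 mg/kg IV) will be administered; a pre-dose blood sample will be taken". Appendix 6b numbers these unscheduled samples in a 500 series (Arm 2) and a 600 series (Arm 3). The scheduled pre-dose samples are in Appendix 6a.

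**The summary.** Protocol 12.5.3 states: "Descriptive summary statistics will be provided by treatment and visit/sampling time point". SAP 2.8 keeps this, and adds that "CFZ533 plasma concentration data will be listed by treatment, participant, and visit/sampling time point using PKS". Neither section mentions unscheduled samples.

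**The window rule.** SAP 5.1 says that "all data (including reported unscheduled assessments) are" re-aligned to the windows of Table 5-1, and SAP 2.1 says that these windows are the ones used for analysis. Continuous values normally take the measurement closest to the target day. CFZ533, TAC and MMF trough measurements are exempted by name: "For trough levels, the last value observed within a visit window is taken".

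**The PK set.** SAP 2.1.2 requires "no protocol deviations that impact on PK data, e.g. if a dose was taken more than 7 days after the planned date". Compensation is directed by the protocol, so it is not a deviation and does not remove these participants.

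**The concern.** A trough in a by-visit table should be the concentration just before a scheduled dose, at the same point of the dosing interval for everyone. A sample triggered by 4 L of drainage can fall anywhere in that interval, and drug has just been removed with the fluid. Both kinds of sample are labelled pre-dose, so the label does not separate them. The last-value rule then prefers the off-schedule sample whenever it is the later of the two, and the scheduled trough drops out of the table.

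Free CFZ533 concentration over time is the endpoint of a stated secondary objective, which includes the dose-exposure relationship (Protocol Table 2-1). SAP 2.8 retains it in the reduced analysis after early termination. What is at stake is whether the by-arm trough table in the report contains troughs.

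**Working it through.** **1. The plan's own figures.** The text to Protocol Figure 4-2 puts the first compensatory dose on Study Day 16 at 0.5 L/day: 4 / 0.5 = 8 days, and 8 + 8 = 16. This reproduces. The cumulative doses in Protocol 4.2.1 also reproduce at 70 kg and 75% bioavailability: 30 x 70 + 15 x 70 + 600 x 0.75 = 3600 mg to Day 29, and 3600 + 2 x 450 = 4500 mg to Day 57.

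**2. Interval between unscheduled samples.** Interval = 4 L / daily drained volume: 4 days at 1 L/day, 8 days at 0.5 L/day, 16 days at 0.25 L/day.

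**3. Room for displacement (SAP Table 5-1, days from first treatment).** Taking the scheduled sample at the midpoint, a later sample displaces it if it falls between the midpoint and the window end.

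| Visit | Window | Midpoint | Days after midpoint |
|---|---|---|---|
| Month 1.5 | 30-43 | 36 | 7 of 14 |
| Month 2 | 44-57 | 50 | 7 of 14 |
| Month 3 | 72-85 | 78 | 7 of 14 |
| Month 4 | 100-113 | 106 | 7 of 14 |
| Month 6 | 156-190 | 162 | 28 of 35 |
| Month 8 | 191-246 | 218 | 28 of 56 |
| Month 12 | 303-358 | 330 | 28 of 56 |

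The Day 29 window also runs 7 days past its midpoint (22 to 29). As an example, take a Month 2 trough drawn on day 50 and a pre-compensation sample on day 54. The closest-to-target rule keeps day 50. The trough rule keeps day 54.

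**4. How many participants.** Protocol 4.3 reports that "a non-negligible proportion of participants (7%) present with a median volume of 1 L/day for a median duration of 77 days" after transplantation. If this share applies here and all the fluid is drained, 0.07 x 48 = 3.4 participants per CFZ533 arm. The chance of at least one per arm is 1 - 0.93^48 = 0.97.

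**5. When.** First treatment is nominally post-transplant Day 8, so Table 5-1 day = post-transplant day - 7. The median end of ascites is day 77 - 7 = 70, near the end of the Month 2.5 window (58-71). Exposure to the problem is therefore mainly at early visits.

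**6. Direction.** The displacing sample contains none of the dose that follows it. It is lowered by the drainage, may be raised because it is drawn before the dosing interval ends, and may be raised or lowered by the balance of earlier loss and compensation. The ascites-to-plasma ratio is not given. At an assumed 0.25 to 1, 4 L at the predicted troughs removes:
- Arm 2 (200 ug/mL): 200 to 800 mg, against 10 x 70 = 700 mg given.
- Arm 3 after Day 29 (100 ug/mL): 100 to 400 mg, against 5 x 70 = 350 mg given.

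The net effect can go either way.

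**7. Size at one visit.** Suppose m of 48 values are multiplied by f. The shift of the mean is (m/48)(f - 1), and that of the geometric mean is f^(m/48) - 1. The median was simulated (20,000 runs, lognormal, assumed CV 40%). The range of f, 0.5 to 2.5, is an assumption.

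| Affected | Mean | Geometric mean | Median |
|---|---|---|---|
| 3 of 48 (7%) | -3.1% to +9.4% | -4.2% to +5.9% | -2.8% to +3.2% |
| 7 of 48 (15%) | -7.3% to +21.9% | -9.6% to +14.3% | -7.0% to +8.4% |
| 14 of 48 (30%) | -14.6% to +43.8% | -18.3% to +30.6% | -15.5% to +21.5% |

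Only the 7% has a source in the documents. The other rows are there because the share reaching 4 L of drainage is not stated. SD, CV, minimum and maximum are more exposed than the median, because a single displaced value can set an extreme.

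**The case against.** **The text can be read the other way.** Summarising by visit and sampling time point may be meant to keep unscheduled samples apart. They have their own number series, and Appendix 6b gives them all Dose Reference ID 1, whereas scheduled samples also carry a dose-specific reference. No section calls a pre-compensation sample a trough. Applied to every concentration, the last-value rule would also replace Arm 2's Day 15 pre-dose value by the one-hour post-infusion value, which cannot be intended. This stands as evidence that displacement may not be wanted. It does not amount to a rule: SAP 5.1 expressly brings unscheduled data into the windows and names CFZ533 in the exception, and nothing excludes the 500 and 600 series.

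**The raw data remain visible.** Concentrations are listed by participant, and Protocol 8.5.2 derives elapsed time since the last dose. That is true, so the problem can be detected, but the summary table would still be wrong for those affected.

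**The effect is small and drives no decision.** This also stands. The summaries are descriptive, and SAP 1 reports that the study was terminated early, with development in this disease area no longer favoured. An argument from future dose selection carries little weight now.

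**Conclusion.** As written, SAP 5.1 lets an unscheduled pre-compensation sample displace a scheduled CFZ533 trough in the by-visit summaries. At the only share the documents give, about 3 of 48 participants per CFZ533 arm are affected. The median shifts by about 3% in either direction and the mean by -3% to +9%. This rests on the 7% applying here, on all ascites being drained, on the assumed factors and CV, and on all affected participants being displaced at the same visit. The primary decision rule is untouched.

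Three stronger readings are tempting but not supported:
- **That pooled summaries do not describe the 300 mg and 600 mg regimens.** Compensation is part of both CFZ533 arms (Protocol 6.1.4 and 6.5.1), so pooling describes each regimen as administered. Separating participants by compensation would condition on a post-randomization event.
- **That every early window is displaced in affected participants.** A sample every 4 days against 7 post-midpoint days suggests this only while drainage continues at 1 L/day. That volume and the 77 days are medians. The post-midpoint days of Month 3 (79-85) are post-transplant Days 86-92, already past the median duration.
- **That compensation must inflate exposure because the extra doses are large beside the scheduled ones.** That comparison ignores drug lost. In Arm 3 at 1 L/day for 14 days, with ascites at 100 ug/mL, 1400 mg is lost against 3.5 x 350 = 1225 mg given.

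**What to change.** In SAP 5.1 and 2.8:
1. State that by-visit CFZ533 trough summaries use only the scheduled pre-dose samples of Appendix 6a. A window without such a sample contributes no trough for that participant.
2. Exclude the 500- and 600-series samples from the last-value rule and list them separately.

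Optionally, mark in the concentration listing which participants received compensatory doses. Also optionally, reconcile Protocol 12.4.1, which asserts that "this unscheduled administration will not result in exposure higher than that seen in participants with no ascites", with SAP 2.4.1, which gives this only as an aim. Protocol 4.3 describes the post-Day 29 prediction but does not show it. No dose rule is proposed.

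The cost is SAP wording and programming. The sample numbers already separate the two kinds of sample, no new data are needed, and no concentration is lost from the listings.
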